4.9. Data Analysis

Data collected from the surveys will be reported as descriptive statistics. Frequency distributions with 95% CIs will be calculated for respondent responses to all questions that address the survey objectives. Depending on the sample size, survey data will be stratified by country and, for HCPs, medical speciality.

4.10. Milestones

The study will be implemented within 12 to 18 months of product launch in the UK (if product uptake does not allow for participation, another comparable EU country will be selected),

**Non-Interventional Study Protocol
for Humalog 200 units/ml KwikPen
Version 1.0**

Germany, and one additional EU country. The timing and countries chosen is dependent on launch dates and the uptake of the product in each country. Findings from the surveys will be reported to regulatory authorities as required.

5. Amendments and updates

Not applicable.

6. Milestones

Milestone	Planned Timeline*
Start of data collection	Within 12-18 months from product launch in the applicable country, depending on launch dates and the uptake of the product in each country.
End of data collection	When the desired number of surveys have been completed.
Registration in the EU Post-Authorisation Safety Studies (PASS) register	Prior to start of data collection
Final study report	Within 12 months after the end of data collection

*The study will be initiated after the distribution of the additional risk minimisation measures) across the 3 study countries and protocol review by PRAC. Therefore, the planned timeline is contingent upon the date of the approval of the RM tools by the local Health Authorities.

7. Rationale and background

Diabetes, especially T2DM is increasing in global prevalence and associated economic and humanistic burdens. Despite tangible improvement in disease management, poor glycaemic control remains a problem in individuals with diabetes (Inzucchi et al, 2012). Diabetes management guidelines recommend early initiation of insulin therapy in individuals with poor T2DM control or those with poor response to other anti-diabetes medications (Petznick A, 2011; ADA, 2014). In addition, insulin resistance and progressive loss of pancreatic beta-cell function are prodromal features of T2DM, which partially contribute to the need for high-dose insulin therapy—worldwide, about 30% of patients using basal insulin require more than 60 units daily (Gough et al, 2013), and approximately half of patients with T2DM will eventually require insulin to manage their diabetes (Jabbour, 2008).

Hypoglycaemia is an identified risk of insulin therapy, and compared to other anti-diabetes medications, hypoglycaemia risk is the highest with insulin (Maria Rotella et al, 2013). Hypoglycaemia may occur due to low carbohydrate intake, alcohol consumption, exercise, or stress. On the other hand, failure to receive an adequate amount of insulin can result in hyperglycaemia and poor diabetes control (Cornish, 2014). Hyperglycaemia may occur due to excessive carbohydrate intake, less than planned exercise, or stress. Additionally, medication errors may contribute to these two conditions.

Insulin formulations are listed among the high-alert medications that have the potential to cause significant patient harm due to medication errors—in hospital setting, about 24% of insulin errors contributed to patient harm and 33% of deaths due to medication errors were attributed to insulin therapy (Cobaugh et al, 2013). Insulin medication errors occur across the continuum of medication-use process; however, prescribing and administration related medication errors are most common (Cobaugh et al, 2013). Medication errors involving insulin may include inadvertent interchange between insulin strengths or formulations, incorrect dosage, or incorrect use of pen-injector devices. These errors may result in hyper/hypoglycaemia.

Humalog 200 units/ml KwikPen is a prefilled and multi-dose pen-injector device (pen) that delivers by subcutaneous injection insulin lispro for the maintenance of normal glucose homeostasis in adults with diabetes mellitus. Compared to Humalog 100 U/ml, it contains the same number of units of insulin lispro in half the volume. Despite warning messages on the pen and in the instructions for use, results from Human Factors studies performed in the US showed that a small percentage of patients may choose to withdraw insulin from the pen cartridge with a syringe if faced with device malfunction. Anecdotal information also indicates that patients in the EU may transfer insulin lispro from the pen cartridge into an insulin pump. Because of these data and to further optimise the benefit-risk balance of the formulation, additional Risk Minimisation Measures beyond routine risk minimisation measures (are being implemented, including communications to HCPs and patients to minimise the risk of hypoglycaemia and/or hyperglycaemia associated with insulin transfer from the pen cartridge to an alternative administration device without concentration adjustment and dose adjustment when transferring from Humalog 100 U/ml to Humalog 200 units/ml KwikPen.

**Non-Interventional Study Protocol
for Humalog 200 units/ml KwikPen
Version 1.0**

The additional risk minimisation measures include a DHPC that will be distributed to all physicians and nurses who are expected to be involved in the treatment and management of patients with diabetes and, where required, all pharmacists who are expected to dispense Humalog 200 units/ml KwikPen (HCPs). A patient communication document will be distributed to HCPs targeted for the DHPC. The DHPC will ask the HCPs to provide the patient communication to patients receiving their initial prescription of Humalog 200 units/ml KwikPen. Where approved, a web address link to the patient communication may also be provided in the DHPC to allow either printing of the communication during the patient visit or provision of the link to the patient to enable the patient to directly access the communication.

8. Research question and objectives

This primary study objective is to evaluate the impact of the risk minimisation measures on HCP and patient understanding regarding the risk of hypoglycaemia and/or hyperglycaemia due to medication errors associated with administration of Humalog 200 units/ml KwikPen as communicated through the risk minimisation measures.

The secondary objective is to evaluate behaviour of HCPs and patients regarding the risk of hypoglycaemia and/or hyperglycaemia due to medication errors associated with administration of Humalog 200 units/ml KwikPen as communicated through the risk minimisation measures.

Specifically, this protocol refers to the surveys that are designed to assess the effectiveness of communications to HCPs and patients by assessing their understanding of the risks and safe use of Humalog 200 units/ml KwikPen which were communicated through risk minimisation measures including the following key messages:

HCPs:

- It is not necessary to adjust the insulin dose when switching from one strength of Humalog to the other
- Humalog 200 units/ml should not be transferred from the KwikPen to alternative administration devices
- It is necessary to specify the Humalog strength on prescriptions

Patients:

- It is not necessary to adjust the insulin dose when switching from one strength of Humalog to the other
- Humalog 200 units/ml should not be transferred from the KwikPen to alternative administration devices

The surveys are also designed to answer the following process research questions to assess the effectiveness of communications to HCPs and patients through the risk minimisation measures. By testing a representative population about their knowledge and understanding of key message themes, we can generalise the:

HCPs:

- Extent of understanding of the key safety messages for Humalog 200 units/ml KwikPen, as communicated through the DHPC (Were the key safety messages communicated in the HCP communication understood by the HCP?)
- Extent that the patient communication has been provided to patients (Was the patient communication or the means to access the patient communication provided to each patient upon first prescription of Humalog 200 units/ml KwikPen?)

**Non-Interventional Study Protocol
for Humalog 200 units/ml KwikPen
Version 1.0**

- Extent of discussion between HCPs and patients when initially prescribing or dispensing Humalog 200 units/ml KwikPen (Did the HCP convey the key safety messages in the patient communication to patients when they received their initial prescription of Humalog 200 units/ml KwikPen?) with reference to the following safety messages.

Patients:

- Extent of understanding of the key safety messages for Humalog 200 units/ml KwikPen, as communicated through risk minimisation measures (Were the key safety messages in the patient communication understood by the patient?)
- Extent of recall/receipt of the patient communication or the means to access the patient communication from prescribers upon first prescription of Humalog 200 units/ml KwikPen (Does the patient recall receiving the patient communication document or the means to access from their HCP?)
- Extent of key safety message consideration by patients during administration of Humalog 200 units/ml KwikPen (Will the patient consider the safety messages communicated during administration of Humalog 200 units/ml KwikPen?)

9. Research methods

9.1. Study design

This study is a multi-national, observational, cross-sectional survey design. Separate surveys will be administered to HCPs involved in the treatment and management of patients with diabetes and to patients with diabetes who have been prescribed Humalog 200 units/ml KwikPen. The study has been designed and will be executed and analysed in collaboration with UBC. The surveys have been developed to enable the study objectives to be met (Section 8).

User Testing was performed on each survey with a sample of 10 HCPs and 9 patients. The User Testing procedure was designed to assess comprehension among patients regarding the words and phrases used in select survey questions and response options. User Testing also assessed the clarity of the survey questions as presented to HCPs and the interest and acceptance of the surveys among all prospective respondents, flow and ease of completing the surveys, and preferred modes of administration. Findings and recommendations from User Testing have been incorporated into the surveys.

Assessment of the additional risk minimisation measures in the participating samples will be used to determine whether the target populations are aware of and adherent to the key message themes regarding the risk of hypoglycaemia and/or hyperglycaemia attributed to medication errors or misuse associated with the administration of Humalog 200 units/ml KwikPen. All statistical analyses will be descriptive, that is, no formal hypothesis will be tested. Study endpoints are as follows:

The tools will be considered effective if the majority of respondents demonstrate they are aware of the key risks communicated.

HCPs:

- Demonstrating that they understand the key safety messages communicated in the DHPC
- Reporting that they provided the patient communication or means to access the communication to patients at the time of first Humalog 200 units/ml KwikPen prescription
- Reporting they discussed the key safety messages in the patient communication with their patients who are receiving their first prescription of Humalog 200 units/ml KwikPen

Patients:

- Demonstrating that they understand the key safety messages communicated
- Reporting that they were provided with a copy of or means to access the Humalog 200 units/ml KwikPen patient communication from their HCP at the time of initial prescription
- Reporting that they consider the key messages during administration of Humalog 200 units/ml KwikPen

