4.5. Study Endpoints

The additional risk minimisation measures will be considered effective if the majority of respondents demonstrate they are aware of the key risks communicated.

HCPs:

- Demonstrating that they understand the key safety messages communicated in the DHPC
- Reporting that they provide patients with a copy of or means to access the Humalog 200 units/ml KwikPen patient communication at the time of initial prescription
- Reporting they discuss the key safety messages in the patient communication to their patients who are receiving their first prescription of Humalog 200 units/ml KwikPen.

Patients:

- Demonstrating that they understand the key safety messages communicated about Humalog 200 units/ml KwikPen

- Reporting that they were provided with a copy of or means to access the Humalog 200 units/ml KwikPen patient communication from their HCP at the time of initial prescription
- Reporting that they take into account the key messages during administration of Humalog 200 units/ml KwikPen.

All statistical analyses will be descriptive, that is, no formal hypothesis will be tested.

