- HCP medical specialty (for example, endocrinology, primary care)
- Number of years practicing medicine/nursing
- Number of Humalog 200 units/ml KwikPen-treated patients the HCP managed in the 12 month period preceding the survey (self-reported)

Data pertaining to evaluation of the effectiveness of the risk minimisation measures:

The survey includes questions/statements that will assess the risk understanding and behaviour of the HCPs. The understanding level and behaviours will be analysed using descriptive statistics and CIs and will be used to determine the effectiveness of the risk minimisation measures:

- Awareness of the DHPC on the correct use of Humalog 200 units/ml KwikPen
- Understanding of the key risk messages

- Self-reported practices with respect to communication of the key risk messages in clinical practice

Patients:

Screening questions:

- Agreement to participate
- Diagnosis of diabetes
- Prescribed Humalog 200 units/ml KwikPen
- 18 years or older
- Prior or current employment by Lilly, UBC, or any national medical governing body, such as but not limited to EMA, MHRA, and BfArM

Data on demographic characteristics:

- Age
- Sex
- Country
- Education status
- Length of time with diabetes
- Length of time on any insulin therapy
- Length of time on Humalog 200 units/ml KwikPen
- Length of time on Insulin used prior to Humalog 200 units/ml

Data pertaining to evaluation of the effectiveness of the risk minimisation measures:

The survey includes questions/statements that will assess the risk understanding and behaviour of patients. The understanding level and behaviours will be analysed using descriptive statistics and CIs and will be used to determine the effectiveness of the risk minimisation measures:

- Awareness of the Important Safety Information for Humalog 200 units/ml KwikPen
- Receipt of or access to the Important Safety Information
- Understanding of the key risk messages
- Patient behaviour with respect to the key risk messages

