9.5. Study size

The target sample sizes for the HCP and patient populations are 280 completed surveys for each population. This sample size was determined based on the width of confidence intervals it will provide. [Table 1](#) shows 2-sided 95% confidence intervals based on the normal approximation to the binomial distribution ([Equation 1](#)) for a single sample of size of 280.

The samples will be divided by countries according to the distribution of eligible participants in each country. The EDC system will be programmed with country-specific limits to ensure desired distribution. Both unweighted and weighted results will be presented in the final report.

Equation 1.

$$95\%CI = Response\ Rate \pm 1.96 \left\{ \sqrt{\left[\frac{Response\ Rate(1-Response\ Rate)}{Sample\ Size} \right]} \right\}$$

Table 1. Sample size calculations

Sample Size	Observed Response Rate* (e.g. Knowledge)	2-Sided 95% Confidence Interval		
		Half-width	Lower Limit	Upper Limit
280	50%	5.9%	44.1%	55.9%
	60%	5.7%	54.3%	65.7%
	70%	5.4%	64.6%	75.4%
	80%	4.7%	75.3%	84.7%
	90%	3.5%	86.5%	93.5%

*Percentage of responders who correctly answered a question.

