- Some secondary school (or EU equivalent) or less
 - Finished secondary school
 - Some university or completed technical/trade school
 - Graduated university
 - Post graduate studies
 - Prefer not to answer
11. In what country do you live?
- [DROP-DOWN LIST INPUT WITH COUNTRIES TABLE]**
12. Which of the following groups best describes your age?

- Under 18 **[TERMINATE AFTER Q12]**
 - 18 – 29
 - 30 – 39
 - 40 – 49
 - 50 – 59
 - 60 – 69
 - 70 or older
 - Prefer not to answer **[TERMINATE AFTER Q12]**
13. Have you or any of your immediate family members ever worked for Eli Lilly and Company (Lilly), United BioSource Corporation (UBC), or the European Medicines Agency (EMA)?
- Yes **[TERMINATE]**
 - No
 - I don't know **[TERMINATE]**

[END SCREENING QUESTIONS]

[BEGIN SURVEY CONTENT]

[PREAMBLE 2]

The following questions are about Humalog 200 units/ml KwikPen.

14. Please answer True, False, or I don't know for each of the following statements about Humalog 200 units/ml KwikPen.

	[RANDOMISE LIST]	True	False	I don't know
A	Humalog 200 units/ml should only be injected using the			

prefilled KwikPen device in which it is supplied.

- B Your dose of insulin does not need to be converted when changing from one strength of Humalog to the other (for example, changing from Humalog 100 U/ml to Humalog 200 units/ml KwikPen).

15. Please answer Yes, No, or I don't know for each of the following statements about the patient communication titled *IMPORTANT SAFETY INFORMATION FOR Humalog 200 units/ml KwikPen (insulin lispro)*.

- | | Yes | No | I don't know |
|---|-----------------------|-----------------------|-----------------------|
| 
[RANDOMISE LIST]
 
[DISPLAY ONLY IN [ENTER COUNTRIES THAT DO NOT HAVE WEBSITE]]The first time I was prescribed Humalog 200 units/ml KwikPen, my doctor or nurse provided me with a paper copy of IMPORTANT SAFETY INFORMATION FOR Humalog 200 units/ml KwikPen (insulin lispro).
 |  |  |  |
| 
A [DISPLAY ONLY IN [ENTER COUNTRIES THAT HAVE WEBSITE]]The first time I was prescribed Humalog 200 units/ml KwikPen, my doctor or nurse provided me with a paper copy or told me to access the website to view IMPORTANT SAFETY INFORMATION FOR Humalog 200 units/ml KwikPen (insulin lispro).
 |  |  |  |

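### Both patient knowledge statements have True as the correct answer, so agreement cannot be told apart from understanding and yes-saying can meet the majority criterion

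*Protocol*

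**What the plan says.** The success rule appears twice in near-identical terms. Section 9.1 has "The tools will be considered effective if the majority of respondents demonstrate they are aware of the key risks communicated" and Section 4.5 has "The additional risk minimisation measures will be considered effective if the majority of respondents demonstrate they are aware of the key risks communicated". Section 9.1 adds "All statistical analyses will be descriptive, that is, no formal hypothesis will be tested". Section 9.4 says that understanding and behaviour "will be analysed using descriptive statistics and CIs and will be used to determine the effectiveness" of the measures, but no section ties a confidence limit to the verdict. No section says whether the majority applies to each item or to all items together.

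Patient understanding is part of the primary objective. Section 8 gives patients two key messages: no dose adjustment between Humalog strengths, and no transfer of the 200 units/ml product out of the pen. Appendix I.3 tests these with one item each:

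- Q14A begins "Humalog 200 units/ml should only be injected using the" and goes on to name the prefilled pen.
- Q14B reads "Your dose of insulin does not need to be converted when changing from one strength of Humalog to the other", followed by an example.

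The response options are True, False and I don't know. Section 9.7 generally scores I don't know as incorrect. On the planned size, Section 9.5 states "The target sample sizes for the HCP and patient populations are 280 completed surveys for each population".

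**The concern.** Read against Section 8, Q14A and Q14B both restate a key message in the affirmative, so True is correct for both. A patient who tends to agree with statements in a safety survey gets full marks without having read or understood the communication.

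Nothing else in the design separates the two. Randomising the order of statements (Sections 9.4.1 and 9.9.1) does not change which answer is correct. User testing in 9 patients (Section 9.1) is described as covering comprehension of wording, flow, acceptance and mode, not whether the items discriminate. The limitations in Section 9.9 cover self-selection, recall and self-report, but not a tendency to agree. The cross-sectional design has no baseline or unexposed group from which an agreement rate could be estimated and subtracted.

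At stake is the patient half of the primary objective. A finding of effectiveness reported to regulators could reflect agreement with the statements, not knowledge of a medication-error risk.

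**Working it through.** **Inputs from the protocol.** n = 280 patients (Section 9.5); success is a majority (Sections 4.5 and 9.1); two items, both with True as the correct answer (Appendix I.3 read with Section 8); I don't know generally scored incorrect (Section 9.7).

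**Inputs assumed.** The protocol gives no agreement rate. Let k be the share of patients who know both messages and y the share, among all patients, who answer True to both without knowledge. The rest choose I don't know.

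**Step 1: the plan's own figures.** Section 9.5 "shows 2-sided 95% confidence intervals based on the normal approximation to the binomial distribution". With half-width = 1.96 × √(p(1 − p)/280), observed rates of 50, 60, 70, 80 and 90% give 5.86, 5.74, 5.37, 4.69 and 3.51 points. These round to Table 1 (5.9, 5.7, 5.4, 4.7, 3.5).

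**Step 2: the pass mark.** The smallest majority is 141/280 = 50.4%. Its half-width is 5.86 points, so the interval is 44.5% to 56.2%.

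**Step 3: yes-saying.** With both items keyed True, the share with both correct is k + y, and each item separately gives the same share. The chance of a majority is P(X ≥ 141) for X ~ Binomial(280, k + y). If one item were keyed False, a patient who always answers True would get that item wrong, and the both-correct share would be k.

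| k | y | both correct as drafted (k + y) | P(majority) | both correct with one item keyed False (k) |
|---|---|---|---|---|
| 0 | 0.4 | 40% | 0.0003 | 0% |
| 0 | 0.5 | 50% | 0.476 | 0% |
| 0 | 0.6 | 60% | 0.9996 | 0% |
| 0.2 | 0.2 | 40% | 0.0003 | 20% |
| 0.2 | 0.3 | 50% | 0.476 | 20% |
| 0.2 | 0.4 | 60% | 0.9996 | 20% |

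Because each yes-sayer scores on both items, these probabilities are the same whether the majority is applied per item or to both items together.

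**Step 4: would a confidence-limit rule cure it?** The smallest count whose lower 95% limit exceeds 50% is 157/280 = 56.1%. With k = 0 and y = 0.6, P(X ≥ 157) = 0.92. A stricter threshold therefore leaves most of the problem in place.

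**Step 5: guessing, for comparison.** The chance that one item reaches 141/280 with no knowledge at all is:

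- 0.476 if nobody uses I don't know and guesses split evenly (p = 0.50);
- 0.041 if 10% choose I don't know and the rest split evenly (p = 0.90 × 0.5 = 0.45);
- about 3 × 10⁻⁹ if guesses are uniform over three options (p = 1/3).

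If both items must be right, independent even True/False guessing gives p = 0.5 × 0.5 = 0.25 and a probability of about 8 × 10⁻²⁰.

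**The case against.** Several points on the other side have force.

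- **The agreement rate is assumed, and the result is sensitive to it.** Suppose non-knowers choose I don't know 30% of the time and otherwise answer True 75% of the time. Expected correct per item is 0.70 × 0.75 = 52.5%, and the pass probability is 0.78. Lower the 75% to 60% and expected correct is 42%, with a pass probability of 0.003. Lower the 30% to 20% instead and they are 60% and 0.9996. This stands: the size is conditional. The direction is not, since yes-saying can only raise the score as drafted.
- **A reader might infer that guessing alone would pass the criterion about half the time.** The documents do not support this. I don't know is offered and generally scored incorrect, so the 0.476 figure needs almost every non-knower to avoid it and the rule to apply per item.
- **A reader might infer that a bare point estimate decides the verdict, or that a single message passing is enough.** Neither is written. Section 9.4 brings confidence intervals into the judgement, though without a rule, and the success wording refers to the risks in the plural. The unit is unclear, and a statistical analysis plan may settle it.
- **A reader might extend the point to the whole study.** The HCP knowledge questions are not in the text available, so nothing can be said about their keying.
- **Regulators will see item-level frequencies with intervals (Section 9.7), not only a verdict.** True, but those frequencies carry the same agreement bias and cannot reveal it.

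What remains is the keying itself. An analysis plan can define thresholds and units, but it cannot re-key a questionnaire that has already been answered.

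**Conclusion.** The point holds for the patient survey. Both knowledge items have True as the correct answer under the protocol's own key messages, so the measure of understanding is confounded with a tendency to agree. In the simple model above, the majority criterion is more likely than not to be met once knowers and yes-sayers together clearly exceed half of patients. At 60% in total it is met almost surely (0.9996), whether those patients know the messages or merely agree.

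This rests on an assumed agreement rate and on non-agreeing non-knowers choosing I don't know. It does not show that patients will in fact yes-say at that level, only that the instrument could not detect it if they did. It is an avoidable weakness in the instrument and is cheap to correct while the survey is a draft. A confidence-limit rule for the majority is an optional choice in a study declared descriptive, and it does not remove the problem.

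**What to change.** Before fielding, change Appendix I.3 in one of two ways:

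1. Re-key one of Q14A and Q14B so that its correct answer under the existing key message in Section 8 is False, for example by stating Q14B without its negation; or
2. keep both and add a paired reverse-keyed statement.

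The key messages themselves stay as they are; only the form of the test item changes. In Section 9.7, add the share of patients with all knowledge items correct, reported beside the per-item results. A patient who answers True throughout then cannot count as fully correct, and a gap between the True-keyed and False-keyed items would make agreement visible.

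It would also help to say in Sections 4.5 and 9.1 whether the majority applies per message or to all messages, but this is secondary.

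Cost: a brief wording re-test, since the current items have already been through user testing, and translation of one item for the study countries (Section 9.2). No extra respondents are needed. Annex 1 still lists the patient survey as a draft.
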